## I. Abstract

Short bowel syndrome (SBS) following massive bowel resection for various conditions, especially necrotizing enterocolitis (NEC), is a devastating complication that affects neonates especially those delivered < 36 weeks gestational age. These children are especially susceptible to recurrent blood stream infections (BSI), repeated hospital admissions and subsequent poor growth. All of these contribute to a very high burden on the primary caretakers and the health care system. Organisms associated with recurrent BSI in these children are predominantly gut related. However, there is still a lack of understanding of the intestinal microbial ecology of these children and whether it has a role in BSI, enteral feeds and ultimately growth. Glutamine (GLN) supplementation has been shown to decrease mucosal damage, lower rates of BSI and associated sepsis and improve positive nitrogen balance in adults with SBS. In children, there is currently insufficient data to determine whether enteral GLN supplementation improves clinical outcomes in young infants with significant gastrointestinal resection leading to SBS. The overall purpose of this pilot clinical study is to obtain needed preliminary data on the efficacy of enteral GLN supplementation in children with SBS as a result of significant intestinal resection due to NEC, omphalocele, gastroschisis and intestinal atresia in the context of a rigorous, double-blind exploratory clinical trial with the following specific aims: **Specific Aim 1:** To perform a double-blind, randomized, placebo controlled, 6-months pilot study of enteral GLN treatment in PN-dependent SBS children due to NEC, omphalocele, gastroschisis and/or atresia evaluating the efficacy of enteral GLN supplementation to decrease BSI and serial serum concentrations of TNF- $\alpha$ , IL1-  $\beta$ , IL-6 and IL-8; **Specific Aim 2:** To assess the efficacy of 6 months of therapy with enteral GLN as a method to improve somatic growth parameters (length velocity, weight velocity, head circumference and mid arm circumference) in Aim 1 subjects and the impact of BSI on growth parameters; **Specific Aim 3:** To comprehensively assess the gut luminal microbiome (using state-of-the art molecular methods) in Aim 1 pediatric SBS patients versus non-SBS, age-matched controls, and, in the SBS patients to correlate major bacterial populations present in the lumen with BSI due to these microbes and to explore whether the gut luminal microbiome is altered by enteral GLN treatment. This proposal will facilitate the development of a multicenter, multidisciplinary team from Cincinnati Children's Hospital Medical Center, University of Michigan and University of Colorado to assess new methods for decreasing BSI and improving growth as well as to gain insights into the intestinal microbial ecology of SBS children.

## II. Purpose of Study

This is a double-blind, randomized placebo-controlled pilot study to investigate the efficacy of enteral glutamine (GLN) supplementation in 36 infants,  $\leq 12$  months of age with parenteral nutrition (PN)-dependent short bowel syndrome (SBS) due to massive small bowel resection for NEC, omphalocele, gastroschisis and/or atresia on improving weaning of PN and preventing infections. We intend to evaluate the effect of enteral feeding and GLN supplementation on the gut bacteria. We will also recruit 12 age-matched controls to evaluate the normal gut bacteria. Investigators at the University of Michigan and Cincinnati Children's Hospital Medical Center will recruit the potential subjects (18 patients and 6 controls will be recruited at each site). We will estimate residual small and large bowel length and the presence, or absence of the ileocecal valve and colon by review of surgical records and postoperative intestinal barium studies in the subjects. Estimates of bowel length for gestational age have been previously published. Data on parenteral or enteral GLN supplementation (L-GLN or the dipeptide Alanyl-GLN) in infants have not shown consistent effects, potentially because these studies were under powered; the dose of GLN was suboptimal or other factors.

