## III. Background

### Significance

Pediatric SBS is characterized by insufficient bowel length causing inability to maintain protein, energy, fluid, electrolyte or micronutrient balances when the child is on a conventionally accepted enteral diet. The use of PN is often required in SBS to provide nutrition and sustain life; unfortunately PN does not promote gut adaptation and also predisposes to BSI.

Appropriate management with PN typically prevents nutritional deficiencies, enhances weight gain and is associated with improved overall survival rates. In infants, NEC is the major cause of surgical SBS; other causes include gastroschisis, midgut volvulus and intestinal atresia.

Children with PN-dependent SBS exhibit a high rate of recurrent BSI. The quality of life burden and healthcare costs associated with SBS in affected children is extremely high, in part, due to costs and complications of PN and hospitalizations for BSI. Healthcare costs in the first year of life in pediatric SBS patients routinely exceed \$500,000^12. Inpatient hospitalization accounted for most (>80%) of this expense, attributed to prolonged NICU stay, surgical procedures and recurrent BSI. The cost of home health care in children with SBS increases during each subsequent year of PN use. **In light of the clinical importance of pediatric SBS, the high healthcare-related costs, and the ineffectiveness of current therapy to prevent BSI, new treatments to improve clinical outcomes are urgently required. Data to increase our understanding of the putative causes of BSI in this orphan disease are also needed.**

Recurrent sepsis and prolonged PN are each predictors of increased morbidity and mortality in children with SBS. The very high rate of recurrent BSI in infants with SBS is presumably due to impaired gut and systemic immunity and gut barrier dysfunction. Translocation of indigenous intestinal microbes has been shown to occur in animal models of SBS, with the translocation being promoted by generalized host immunosuppression, gut-associated immune dysfunction and gut barrier dysfunction. The incidence of catheter sepsis is significantly higher in children with SBS than in those without SBS (7.8 vs. 1.3 per 1000 catheter days;

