#### Exclusion criteria for age matched controls

- Major congenital or chromosomal anomalies
- Inability to tolerate enteral nutrition/ regular cow's milk, breast milk or soy formula

- History of liver/intestinal transplantation
- Active milk protein allergy
- Inflammatory bowel disease
- Multiorgan failure

Inclusion Criteria for glutamine and placebo group of SBS patients (n=36; 18 per site)

- Males and females  $\leq$  12 months of age (corrected for gestational age)
- Patients who have undergone small bowel resection due to complications of or related to NEC, omphalocele, gastroschisis or intestinal atresia with known small bowel length
- Patients who have been PN dependent for more than 42 consecutive days (6 weeks) and currently on TPN at time of enrollment. This would include patients who were off TPN for  $<$  7 consecutive days.
- Patients who have the ability to take partial enteral nutrition of at least 5ml/hr breast milk or elemental formula (Elecare® is the preferred formula at both clinical sites but use of other elemental formula does not exclude the patient) (via gastric or intestinal tube, or orally) to allow the appropriate dose of GLN (0.6 g/kg/day) or placebo (L-alanine)
- Signed informed consent for the use of GLN or placebo obtained

Exclusion Criteria for glutamine and placebo group of SBS patients

- Major congenital or chromosomal anomalies
- Inability to tolerate enteral nutrition that will preclude treatment with enteral GLN or L-alanine placebo for  $>$ 2 consecutive weeks
- Liver/intestinal transplantation
- Multiorgan failure

B. Withdrawal Criteria

1. Patient cannot complete evaluation visit assessments
2. Patient develops any of the exclusion criteria detailed above
3. Patient develops significant hepatic dysfunction (defined as INR  $>$  2.5 or direct serum bilirubin level  $>$  10 mg/dL)
4. Parent(s)/legal guardian are unwilling to administer the GLN or placebo at the required dosage
5. Patient is lost to follow-up
6. Patient has 3 missed study visits
7. It is in the patients best interest

C. Dropouts

Data collected from patients who voluntarily withdraw from the study or who are withdrawn from the study will be included in the final analysis using intent to treat. Patient and control enrollment will continue until 32 patients complete all requested study requirements outlined. The reason for withdrawal will be documented.

D. Stopping Rules

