**Study Procedures Table for Control group**

	Screening and Consent	Baseline (Day 0)	60-day visit	120-day visit	180-day visit (final visit)
Signed informed consent	X	X			
Medical History/questionnaire		X	X	X	X
stool collection for bacterial and sIgA analysis		X	X	X	X

I. Data Collection

Demographic and clinical information will be collected whenever clinical data are available via uniform baseline and follow up clinical data extraction forms to ensure accuracy and consistency. The essential demographic information includes age at diagnosis, gender, race and ethnicity, birth history and past medical history. The clinical information includes bowel length, dates and type of surgeries, nutrition data (formula type, amount, weaning foods, parenteral nutrition type and amount), infection type (genus, species and susceptibility to antibacterials) date infection is diagnosed) hospital admissions and hospital length of stay.

J. Compensation

Participants will receive \$10 for every stool collected for analysis during study participation. Subjects will receive study medication, clinical supplies, and laboratory evaluations related to the study free of charge.

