- 1) Plasma proinflammatory cytokine levels: TNF- $\alpha$ , IL1- $\beta$ , IL-6, and IL-8. Change from baseline values at 180 days will be computed for cytokine levels. Change from baseline to 180 days values will also be calculated for the flagellin and LPS IgG levels. Appropriate transformations of the data (e.g. log) will be done prior to calculating change from baseline in order to meet the assumptions of the analyses (i.e. normality, equal variance). Analysis of covariance techniques will be used to compare the change from baseline scores of the treatment groups. Covariates included in the analysis will be baseline value, age, gender, ostomy status, feeding type (formula, breast milk).
- 2) Length of hospital stay and number of readmissions: For length of hospital stay, treatment groups will be compared using the Wilcoxon Rank Sum test. For number of readmissions, either a Wilcoxon Rank Sum test or a Chi-Square test for homogeneity will be used to compare groups, depending on the variability of the number of readmissions.
- 3) Stool sIgA levels: Treatment groups will be compared using the random effects repeated measures analysis of covariance. The response variables for each of the parameters will be change from baseline. The time points included in the analyses will be 30, 60, 90, 120, 150, 180 days post-baseline. If required to meet the assumptions of the analyses (normality, equal variances), appropriate transformations will be used. Treatment groups will be compared at each individual time point using appropriate contrasts and the error term from the repeated measures model. Covariates will include baseline value, age, gender, ostomy status, feeding type (formula, breast milk).
- 4) Proportion of nutrition delivered enterally versus parenterally: The statistically analysis approach for this endpoint will be the same as for the Stool sIgA levels discussed above. Transformations appropriate for proportions may be used, if necessary, to meet assumptions of the analyses.
- 5) Plasma glutamine: The statistical analysis approach for this endpoint will be the same as for the proinflammatory cytokine levels discussed above.
- 6) Impact of level of compliance on outcome will be evaluated for a dose effect analysis.

**Aim 2 Hypothesis:** Enteral GLN supplementation will improve somatic growth parameters in Aim 1 patients.

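### Residual small-bowel length is required at entry and recorded, but the enteral/parenteral proportion and growth models do not adjust for it

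*Combined protocol and SAP*

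**What the plan says.** **Population.** The Purpose of Study section describes infants with short bowel syndrome (SBS) "due to massive small bowel resection for NEC, omphalocele, gastroschisis and/or atresia on improving weaning of PN and preventing infections". The SBS inclusion criteria in section IX.A admit "Patients who have undergone small bowel resection due to complications of or related to NEC, omphalocele, gastroschisis or intestinal atresia with known small bowel length", with no limit in centimetres or percent. They add a functional criterion: "Patients who have been PN dependent for more than 42 consecutive days (6 weeks) and currently on TPN at time of enrollment".

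**Role of length.** Background, Significance: "Pediatric SBS is characterized by insufficient bowel length causing inability to maintain protein, energy, fluid, electrolyte or micronutrient balances".

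**Measurement.** Purpose of Study: "We will estimate residual small and large bowel length and the presence, or absence of the ileocecal valve and colon". The sources are surgical records and postoperative barium studies, and the section cites published length norms by gestational age. Data Collection (IX.I): "The clinical information includes bowel length, dates and type of surgeries".

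**Allocation.** Section IX.H stratifies by site and by whether the colon is in continuity. Feeding type is also taken into account. Small-bowel length is not.

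**Analysis.** In section XIII the stool sIgA model (Aim 1, item 3) and the growth models (Aim 2, item 7) carry the same sentence: "Covariates will include baseline value, age, gender, ostomy status, feeding type (formula, breast milk". The enteral/parenteral proportion (item 4) follows the sIgA model. The cytokine analysis lists the same five covariates, and plasma glutamine follows it. For length and weight velocity the baseline value is baseline body length or weight. Section XIII opens with a baseline comparison by arm but lists no variables for it.

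**The concern.** The trial makes one anatomical quantity a condition of entry, collects it for every infant and ties it to the disease mechanism, but then leaves it out of every outcome model. Ostomy status and colon continuity describe how the bowel is configured. Two infants alike on both can have very different amounts of small bowel.

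The outcomes most exposed are the enteral/parenteral proportion and growth. Length velocity is the Aim 2 primary outcome, and its baseline covariate is body length, which says nothing about the gut. If residual bowel length is prognostic, its contribution stays in the residual error, and a chance difference between two small arms passes into the estimated effect.

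The Sample size section says the pilot is meant to supply effect sizes and variability for a definitive trial. Avoidable residual variance in these models would therefore be carried into that design.

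**Working it through.** **Stated figures first.** All of them reproduce.
- Completers: 18 × 0.9 = 16.2, so 16 per arm.
- Primary outcome: exact enumeration of Fisher's test at 75% versus 30%, 16 per arm, one-sided 10%, gives 85.7% power (stated: at least 85%).
- Cytokines: log-scale SD = √ln(1 + 0.7²) = 0.631. A two-sided 5% t-test of ln 2 with 16 per arm gives 85.2% (stated: at least 80%).

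The primary test is unadjusted, so nothing below changes its power.

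**Inputs.** From the plan: 16 completers per arm, five covariates, two-sided 5% for these outcomes. Assumed, because the documents give no value: R², the share of outcome variance that residual length explains beyond the five covariates, taken from 0 to 0.4. Simplification: one time point instead of the planned repeated-measures model.

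**Chance imbalance.** The standardised difference in mean length between arms has standard error √(2/16) = 0.354. P(|difference| > 0.5 SD) = P(|Z| > 0.5/0.354) = P(|Z| > 1.414) = 15.7%. With all 18 per arm the figure is 13.4%.

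**Size by assumed R².** The standard error falls by 1 − √(1 − R²). The equivalent sample size is 1/(1 − R²). The detectable difference (80% power, noncentral t) uses 25 degrees of freedom without length (32 − 2 − 5) and 24 with it; without length it is 1.03 SD. A 0.5 SD imbalance shifts the unadjusted difference by 0.5 × √R², and dividing by 0.354 expresses that in standard errors.

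| R² | SE cut | Equivalent sample | Detectable difference with length (SD) | Shift from 0.5 SD imbalance |
|---|---|---|---|---|
| 0 | 0% | 1.00 | 1.03 | 0 |
| 0.1 | 5.1% | 1.11 | 0.98 | 0.16 SD (0.45 SE) |
| 0.2 | 10.6% | 1.25 | 0.92 | 0.22 SD (0.63 SE) |
| 0.3 | 16.3% | 1.43 | 0.86 | 0.27 SD (0.77 SE) |
| 0.4 | 22.5% | 1.67 | 0.80 | 0.32 SD (0.89 SE) |

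**Simulation** (4,000 runs per setting, true difference 1.0 SD, five other covariates in the model). Power without and then with length:
- R² = 0: 70.3% and 68.1%
- R² = 0.1: 70.7% and 72.0%
- R² = 0.3: 69.9% and 83.6%

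These powers are lower than the detectable differences suggest because the simulation also charges for chance correlation between covariates and arm: the observed standard error without length is about 0.39, not 0.354. Simulation error is √(0.70 × 0.30/4000) = 0.7 points per figure, so about 1 point on a difference (0.7 × √2). The changes at R² = 0 and 0.1 are therefore rough.

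**Type I error.** Without length in the model the simulated rate was 4.8% to 5.3% for R² from 0 to 0.5.

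**The case against.** The strongest reply is that the gain rests wholly on an assumed R². The Significance text says what makes a patient an SBS patient. It does not say that length predicts outcome among infants already dependent on parenteral nutrition (PN) for more than 42 days. For growth, the Background points to bloodstream infection and cytokines as likely contributors. In the proportion model, the baseline enteral share is itself a measure of gut function, and the colon stratum and ostomy status take up some of the anatomy. What remains for length may be small. All of this stands, and it is why the size is given as a range starting at zero. It is weakest for length velocity, where the baseline value carries no information on the gut.

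A reader might infer more than the documents support:
- *That length is the main driver of weaning and growth.* No passage says so.
- *That any resection qualifies.* No length limit exists, but the PN criterion limits severity functionally. A functional threshold is a design choice.
- *That length enters no analysis at all.* It is absent from the outcome analyses, but the baseline comparison names no variables and may include it.
- *That every interval is widened.* The Fisher, log-rank and Wilcoxon analyses are unadjusted and would not change.
- *That the planned results are biased.* Randomisation protects the type I error. The loss is in precision and in how far a given imbalance can be corrected.

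**Conclusion.** The point holds for the enteral/parenteral proportion and growth models. A baseline value that is required, collected and tied by the protocol to failure on an enteral diet is missing from their covariates.

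Under the assumed 10% to 40% of further variance explained, adjustment is worth a 5% to 23% smaller standard error before one degree of freedom is paid. At 10% the net gain is marginal; at 30% it is substantial. If length explains nothing, the price is about 2 points of power. That trade favours including it, but it is an improvement in efficiency and not the correction of an error: no stated sample-size or power figure is wrong, and the primary comparison is untouched.

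The case is weaker for cytokines, plasma glutamine and sIgA, because the protocol's account of length concerns nutritional balance, so the change need not extend to them. Separately, the word massive describes a population that the entry criteria do not define by length. That is a matter of wording for the conclusions.

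**What to change.** Change the wording of section XIII as follows.

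1. Add residual small-bowel length as one continuous baseline covariate in the enteral/parenteral proportion model (Aim 1, item 4) and the growth models (Aim 2, item 7). Keep the five existing covariates; there is no good reason to drop gender from infant growth models to make room.
2. Fix the scale in advance: either percent of expected for gestational age, naming which of the cited norms applies and the reference age, or absolute length. Use the value established by randomisation.
3. Name residual length in the baseline table and show its distribution by arm.
4. Describe the population as PN-dependent SBS over the residual lengths actually enrolled, in place of massive resection.

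No new data are needed, since a known length is already a condition of entry. The cost is one degree of freedom in each model, about 2 points of power if length proves uninformative. There will also be some measurement error where length comes from barium studies; that reduces the gain but, for a baseline covariate in a randomised comparison, does not bias the treatment effect.

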## III. Background

### Significance

Pediatric SBS is characterized by insufficient bowel length causing inability to maintain protein, energy, fluid, electrolyte or micronutrient balances when the child is on a conventionally accepted enteral diet. The use of PN is often required in SBS to provide nutrition and sustain life; unfortunately PN does not promote gut adaptation and also predisposes to BSI.

Appropriate management with PN typically prevents nutritional deficiencies, enhances weight gain and is associated with improved overall survival rates. In infants, NEC is the major cause of surgical SBS; other causes include gastroschisis, midgut volvulus and intestinal atresia.

Children with PN-dependent SBS exhibit a high rate of recurrent BSI. The quality of life burden and healthcare costs associated with SBS in affected children is extremely high, in part, due to costs and complications of PN and hospitalizations for BSI. Healthcare costs in the first year of life in pediatric SBS patients routinely exceed \$500,000^12. Inpatient hospitalization accounted for most (>80%) of this expense, attributed to prolonged NICU stay, surgical procedures and recurrent BSI. The cost of home health care in children with SBS increases during each subsequent year of PN use. **In light of the clinical importance of pediatric SBS, the high healthcare-related costs, and the ineffectiveness of current therapy to prevent BSI, new treatments to improve clinical outcomes are urgently required. Data to increase our understanding of the putative causes of BSI in this orphan disease are also needed.**

Recurrent sepsis and prolonged PN are each predictors of increased morbidity and mortality in children with SBS. The very high rate of recurrent BSI in infants with SBS is presumably due to impaired gut and systemic immunity and gut barrier dysfunction. Translocation of indigenous intestinal microbes has been shown to occur in animal models of SBS, with the translocation being promoted by generalized host immunosuppression, gut-associated immune dysfunction and gut barrier dysfunction. The incidence of catheter sepsis is significantly higher in children with SBS than in those without SBS (7.8 vs. 1.3 per 1000 catheter days;

p<0.05) and enteric organisms being responsible for 62% of catheter sepsis in patients with SBS compared to only 12% in patients without SBS.

**Preliminary data strongly supports the finding of increased BSI and predominance of enteric organisms in the bloodstream of febrile SBS infants**. The SBS infants in our preliminary data also exhibit elevated levels of proinflammatory cytokines (tumor necrosis factor- $\alpha$ , interleukin 1- $\beta$ , interleukin-6 and interleukin-8) at enrollment vs. control subjects. Previous studies in adults requiring chronic home PN also showed increased blood levels of TNF- $\alpha$  and IL-6.

**Despite receiving adequate calories, SBS infants enrolled in the NICHD Neonatal Research Network had poor growth indices (length and head circumference) and also exhibited a high rate of BSI**. These findings are similar to those previously reported for SBS children requiring long term PN. Catabolic responses due to BSI and elevated systemic cytokines are likely involved in the poor growth exhibited. However, the relationship between BSI and growth failure is conjectural. There are no previous rigorous therapeutic trials designed to decrease BSI and improve growth velocity in infants affected by SBS, as we here propose.

**GLN is a central amino acid in major metabolic processes** and is also utilized as a major fuel/substrate by intestinal mucosal cells and by immune cells, including the gut-associated immune system. During catabolic illness, skeletal muscle exports large amounts of GLN into the blood, and GLN-utilizing tissues, including gut mucosa, immune cells, and kidney markedly increase GLN uptake. If stress persists, GLN requirements may exceed endogenous GLN production, and skeletal muscle and plasma GLN concentrations decline. Numerous studies in animal models show that enteral or parenteral GLN supplementation with either the dipeptide alanyl-GLN or free GLN, enhances gut mucosal growth, repair, and function, decreases gut-origin sepsis and inflammation, and improves nitrogen balance in animal models of intestinal atrophy, injury, and adaptation. Several lines of evidence suggest that GLN may stimulate growth and function of gut mucosal cells in humans. **In adults, GLN has potent anabolic effects, enhances immune functions and decreases nosocomial infection rates**. **In small studies, the combination of enteral GLN, subcutaneously administered human growth hormone and a modified enteral diet improved absorptive capacity and facilitated weaning of PN in adults with SBS**.

Pediatric studies have shown conflicting results regarding the impact of GLN to decrease morbidity and improve somatic growth. **Studies done in clinically stable preterm infants showed that GLN is well tolerated both enterally and parenterally**. Premature infants are susceptible to GLN depletion because placental supply ceases at birth and tolerance to enteral nutrition is limited especially in those with SBS. Current PN in use in the United States does not contain GLN due to solubility and stability issues. Thus, total body GLN depletion may be exacerbated in SBS due to intestinal malabsorption, coupled with inadequate GLN intake, and potentially increased endogenous GLN requirements due to recurrent BSI and other stresses such as surgical trauma. In a group of 69 premature, non-SBS, very low birth weight (VLBW <1500g birth weight) infants between ages 8 and 120 days, enteral GLN supplementation (0.3 g/kg/day) for four months had a significant positive effect on growth indices (weight, length; mid arm, mid thigh and head circumferences). In a randomized, double-blind, controlled single

center trial in 68 VLBW infants, there were no growth or hospital stay difference between the GLN and placebo groups. However, infants receiving GLN had a decreased incidence of sepsis ( $p < 0.05$ ) with risk of infection nearly 4-fold higher in controls. In that study GLN was administered for a median of 27 days. There is limited available data on GLN supplementation in SBS children. In one trial of 20 preterm infants with SBS, due to NEC, intestinal atresia, gastroschisis, omphalocele, intestinal volvulus or malrotation were enrolled. Enteral GLN was administered to only 9 infants at a dose of 0.4g/kg/day up to 120 days, or until full enteral feeds were achieved. GLN was well tolerated, but did not show any benefit on duration of PN use or tolerance of enteral feeds vs. controls. However, given the sample size and diagnosis variability these data should be considered as preliminary.

Although GLN has systemic effects after absorption, the potential effect of this amino acid to decrease BSI and increase protective mucosal immune response in SBS is our goal in this study. *In vitro* studies in human intestinal cell lines show that apical-derived GLN has trophic and cytoprotective effects in both enterocytes and colonocytes, inhibits apoptosis and promotes gut mucosal integrity by markedly attenuating disruption of tight junctions and paracellular permeability. *In vivo* studies in animal models of SBS show that enteral GLN improves indices of gut barrier function independent of its absorption. Investigators have shown that enteral GLN upregulates mucosal and luminal sIgA in rat models.

The available data are inconsistent on the clinical efficacy of parenteral or enteral GLN supplementation (L-GLN or the dipeptide alanyl-GLN) in infants (and more limited data on enteral GLN in pediatric SBS). The reasons for this potentially include underpowered sample size, suboptimal dose of GLN (0.3g/kg/day - 0.5g/kg/day) or other factors. The recommended dose of protein administered to infants is 3.0-3.5 g/kg body weight/day. The dose of parenteral GLN administered to critically ill neonates in a previous NICHD-sponsored multicenter trial was 20% of the total amino acid content of the parenteral nutrition and this GLN dose was well tolerated. We propose to administer enteral GLN at a dose of 0.6g/kg/day, which is approximately 20% of the 3.0-3.5g/kg total protein recommended intake. Doses of 0.5 g/kg/day of enterally administered L-GLN have been well tolerated in clinical trials in infants.

[figure not shown]
